Clinical Development

EMA401

CEMA401A2202 / NCT03297294

A double-blind, placebo-controlled, randomized trial to determine the safety and efficacy of EMA401 100 mg b.i.d. in reducing 24-hour average pain intensity score in patients with painful diabetic neuropathy (EMPADINE)

Statistical Analysis Plan (SAP)

Author: [REDACTED] (CRO), [REDACTED]

Document type: SAP Documentation

Document status: Amendment 1 Final

Release date: 18-Jun-2019

Number of pages: 36

Property of Novartis
For business use only
May not be used, divulged, published or otherwise disclosed
without the consent of Novartis

Document History – Changes compared to previous final version of SAP

Date	Time point	Reason for update	Outcome for update	Section and title impacted (Current)
16-Feb-2018	Prior to FPFV	Creation of final version	N/A – First version	NA
18-Jun-2019	Prior to DB lock	Creation of amendment 1	
 Region names have changed. modified FAS population has been added vitals signs and Friderica's correction have been removed from demographic summary analyses of prior and concomitant medications have partly been revised and described in more detail. Analyses regarding prohibited medications have been removed supplementary analyses regarding the primary endpoint have been reduced. The second supplementary analysis has been kept covariate region has been removed from the ANCOVA model Tipping point analysis has been removed. A sensitivity analysis on the modified full analysis set has been added. Supplementary analyses of responders have been reduced. BPI-SF, PGIC, worst NRS, ISI will be summarized descriptively Temporal items of NPSI will not be summarized descriptively. No summaries of the 5 dimensions of NPSI during the treatment withdrawal period will be provided 	
1.1, Study design, Statistical, hypothesis, model, and method of analysis
 
2.2. Analysis sets
 
2.2.3 Patient disposition, demographics and other baseline characteristics
 
2.4 Treatments (study treatment, rescue medication, concomitant therapies)
 
2.5 Analysis of primary objective
 
2.7 Analysis of secondary efficacy objective(s)
 
2.8.1 Adverse events (AEs)

[figure not shown]

Date	Time point	Reason for update	Outcome for update	Section and title impacted (Current)
			
 Analyses of AEs have been reduced. No subgroup analyses and analyses of drug-related AEs will be provided Dot plots and Kaplan Meier plots of AEs have been removed 	2.8.1.2 Liver events
				2.8.3 Laboratory data
			
 Section has been removed. 	2.8.4 Other safety data
			
 Summary statistics of laboratory parameters, vital signs and ECG intervals will not be presented Shift tables of laboratory data have been removed Bazett correction has been removed 	

List of abbreviations

ACR	Albumin-Creatinine Ratio
AE	Adverse Event
ALP	Alkaline Phosphate
ALT	Alanine Aminotransferase
ANCOVA	Analysis of covariance
AST	Aspartate Aminotransferase
ATC	Anatomic Therapeutic Chemical classification
b.i.d.	twice a day
BPI-SF	Brief Pain Inventory-Short Form
CRO	Contract Research Organization
CSR	Clinical Study Report
DAR	Dose Administration Record
DMC	Data Monitoring Committee
DN4	Douleur Neuropathique en 4 Questions
ECG	Electrocardiogram
eCRF	Electronic Case Report Form
e-diary	Electronic diary
EU	European Union
FAS	Full Analysis Set
FDA	Food and Drug Administration
GGT	gamma-glutamyltransferase
HIV	Human Immunodeficiency Virus
INR	International Normalized Ratio
IRT	Interactive Response Technology
ISI	Insomnia Severity Index
J2R	Jump to reference
LFT	Liver function test
LoE	Lack of efficacy
MAR	Missing at random
mFAS	Modified Full Analysis Set
MedDRA	Medical dictionary for regulatory activities
NPSI	Neuropathic Pain Symptom Inventory
NRS	Numeric Rating Scale
NSAID	Nonsteroidal Anti-inflammatory Drugs
PCR	Protein-Creatinine Ratio
PDN	Painful Diabetic Neuropathy

PHN	Post-Herpetic Neuralgia
PK	Pharmacokinetics
PGIC	Patient Global Impression of Change
PRO	Patient Reported Outcome
█	█
QTc	Corrected QT interval
QTcB	Bazett QT correction formula
QTcF	Fridericia QT correction formula
SAE	Serious Adverse Event
RDO	Retrieved drop-out
SAF	Safety population
█	█
SSRI	Selective Serotonin Reuptake Inhibitor
TBL	Total bilirubin
TD	Study Treatment Discontinuation
TEAE	Treatment-Emergent Adverse Events
ULN	Upper limit of Normal
USM	Urgent Safety Measures
VRS	Verbal Rating Scale
WHO	World Health Organization

Amendment 1

This amendment of the statistical analysis plan (SAP) is largely based on changes induced due to the early termination of the CEMA401A2202 study. 137 patients out of 400 planned patients have been randomized. As the number of patients included in the study is considerably reduced, an abbreviated Clinical Study Report (CSR) that still meets all requirements for reporting and disclosure of the demographics, primary endpoint, secondary endpoints and safety results to public registries will be created.

The primary analysis on the change from baseline to Week 12 in the weekly mean of the 24-hour average pain score will be performed as originally planned. Besides the primary estimand, which is of main clinical interest, the supplementary estimand, which provides insight into the magnitude of improvement in efficacy that might be achieved if all patients were able to take EMA401 as prescribed for 12 weeks, will be analysed. The other planned supplementary estimands will be dropped, as they are of minor interest in the situation with many study treatment discontinuations due to trial termination in the scope of the Urgent Safety Measures (USM).

To support the primary analysis and to get an idea about the effect that might be achieved if the trial had not been terminated and if all patients had the chance to complete the Week 12 assessment, a sensitivity analysis on a modified population will be performed. The modified full analysis set will include all patients who had a chance to complete the study before the termination date, i.e. who had been randomized at least 12 weeks before study termination date.

Similar considerations were made for the key-secondary endpoint.

Due to the considerably reduced number of patients who completed the study, only descriptive subgroup analyses will be provided. Moreover, the secondary endpoints will also be summarized descriptively only.

1 Introduction

This statistical analysis plan (SAP) describes all planned analyses for the Clinical Study Report (CSR) of study CEMA401A2202, a Phase 2, double-blind, placebo-controlled, randomized trial to determine the safety and efficacy of EMA401 in reducing 24-hour average pain intensity score in patients with painful diabetic neuropathy.

The content of this SAP is based on the final version of protocol CEMA401A2202 (release date 15-Sep-2017). All decisions regarding final analysis, as defined in the SAP document, have been made prior to database lock and unblinding of the study data.

1.1 Study design

The study is interventional, randomized, parallel, placebo-controlled, double-blind treatment.

The study will consist of a Screening epoch (up to 4 weeks), a double-blind Treatment epoch (12 weeks), and a double-blind Treatment withdrawal epoch (1 week).

- Patients will be randomized in a 1:1 ratio to treatment with placebo or EMA401 100 mg b.i.d.

Overall approximately 400 patients will be enrolled in the study (i.e. approximately 200 patients will be enrolled in each treatment arm).

At Week 12 (Visit 199), all patients who completed the 12-week double-blind Treatment epoch will enter the 1-week double-blind Treatment withdrawal epoch. The IRT system will indicate the unique medication number for the package of study drug to be dispensed to the patient during the double-blind Treatment withdrawal epoch. This medication number will correspond to the blinded withdrawal regimen assigned at Baseline.

Randomization will be stratified by region (America, Europe and Australia) and use of concomitant pain medication for PDN (yes/no) in order to achieve balance of treatment allocation within the stratification factors.

[figure not shown]
Primary objective of this study is to compare the efficacy of EMA401 vs. placebo in 24-hour average pain intensity score at Week 12, using an 11 point Numeric Rating Scale (NRS) by testing the superiority of EMA401 100 mg b.i.d. vs. placebo.

1.2 Study objectives and endpoints

Table 1-1 Objectives and related endpoints

Objective(s)	Endpoint(s)

Primary Objective(s)
 
 • To compare the efficacy of EMA401 vs. placebo in 24-hour average pain intensity score at Week 12, using an 11 point Numeric Rating Scale (NRS) by testing the superiority of EMA401 100 mg b.i.d. vs. placebo 	
Endpoint(s) for primary objective(s)
 
 • Change in weekly mean 24-hour average pain score (using the 11 point NRS) from Baseline to Week 12

Key Secondary Objective(s)
	
Endpoint(s) for key secondary objective(s)

Objective(s)	Endpoint(s)

 To compare the efficacy of EMA401 vs. placebo in Neuropathic Pain Symptom Inventory (NPSI) total score by testing the superiority of EMA401 100 mg b.i.d. vs. placebo 	
 Change in Neuropathic Pain Symptom Inventory (NPSI) total score from Baseline to Week 12
Secondary Objective(s)	Endpoint(s) for secondary objective(s)

 To evaluate the efficacy of EMA401 compared to placebo, as measured by the Brief Pain Inventory-Short Form (BPI-SF) interference total score at Week 12 To evaluate the efficacy of EMA401 compared to placebo, as measured by the weekly mean of the 24-hour worst pain intensity score, using an 11-point Numeric Rating Scale (NRS) at Week 12 To evaluate the efficacy of EMA401 compared to placebo, on the Patient Global Impression of Change (PGIC) at Week 12 To evaluate the proportion of EMA401 patients achieving a $\geq 30\%$ and a $\geq 50\%$ reduction in weekly mean 24-hour average pain intensity score using the NRS compared to placebo (i.e., responder rates) at Week 12 To evaluate the effect of EMA401 compared to placebo on the Insomnia Severity Index (ISI) at Week 12 To evaluate the safety and tolerability of EMA401 compared to placebo in PDN patients, as measured by treatment emergent adverse events (TEAEs), adverse events (AEs) leading to study drug discontinuation and serious adverse events (SAEs) throughout the study To evaluate the pharmacokinetics (PK) of EMA401 and exposure-response (decrease in pain intensity) relationship for EMA401 throughout the study To evaluate the proportion of patients who need rescue medication separately for the double-blind Treatment epoch and Treatment withdrawal epoch at the time first intake of rescue medication during the double-blind Treatment epoch. 	
 Change in BPI-SF interference total score from Baseline to Week 12 Change in weekly mean of the 24-hour worst pain score, using an 11-point NRS, from Baseline to Week 12 PGIC at end of study Proportion of patients meeting responder criteria from Baseline to Week 12 Change in ISI from Baseline to Week 12 Number and severity of treatment emergent adverse events and the frequency of adverse events leading to discontinuation. Number of serious adverse events. Plasma pharmacokinetics of EMA401 will be characterized by population non-linear mixed effects modeling techniques Proportion of patients who need rescue medication separately for the double-blind Treatment epoch and Treatment withdrawal epoch, the time to first intake of rescue medication during the double-blind Treatment epoch

2 Statistical methods

2.1 Data analysis general information

The statistical analysis of the study will be performed by [REDACTED], a designated Contract Research Organization (CRO).

SAS version 9.4 will be used to perform all data analyses and to generate tables, figures and listings.

Qualitative data (e.g., gender, race, etc.) will be summarized by means of frequency tables; a missing category will be included as applicable. Percentages will be calculated using the number of patients in the relevant population or subgroup as the denominator.

Quantitative data (e.g., age, body weight, etc.) will be summarized by appropriate descriptive statistics, i.e., n, mean, standard deviation (SD), first quartile (Q1), median, third quartile (Q3), minimum, and maximum.

No interim analysis will be performed for the efficacy evaluation. An external Data Monitoring Committee (DMC) will be established with the primary goal to perform an ongoing review of safety data.

2.1.1 General definitions

Investigational drug and study treatment

The investigational drug, EMA401, will be provided as capsules. The following oral dosage strengths will be used: 50 mg.

EMA401 and placebo will be identical in appearance .

For all treatment groups, each dose will be self-administered orally as two capsules with a full glass of non-carbonated water twice daily, consisting of a morning dose and an evening dose.

The following abbreviated treatment groups, independently of cohort number, will be used as the headers in the tables for the double-blind Treatment epoch:

- Placebo b.i.d.
- EMA401 100 mg b.i.d.

The following abbreviated treatment groups will be used as the headers in the tables for the double-blind Treatment withdrawal epoch:

- Placebo b.i.d. -> Placebo b.i.d.
- EMA401 100 mg b.i.d. -> EMA401 100 mg b.i.d.
- EMA401 100 mg b.i.d. -> Placebo b.i.d.

Date of first and last administration of study drug

The date/time of first administration of study drug is defined as the first date/time of administration as per Dosage Administration Record eCRF. The date/time of last administration of study drug is defined as the last date/time when a dose is administered as per Dosage Administration Record eCRF. This value has to be compared to the "End of study treatment" as recorded on the corresponding eCRF. In case of different dates, the latest will be used as treatment end.

For subjects with missing first dose date, the randomization date will be considered as reference start date.

Study day

The study day, describes the day of the event or assessment date, relative to the reference start date which is the date of first administration of study drug.

The study day is defined as:

- The date of the event (visit date, onset date of an event, assessment date etc.) – reference start date + 1 if event is on or after the reference start date.
- The date of the event (visit date, onset date of an event, assessment date etc.) – reference start date if event precedes the reference start date.

Baseline

For safety and efficacy evaluations, the last available assessment (either scheduled or unscheduled) before the first administration of study drug and after the screening visit is defined as “baseline” assessment. If patients have no value prior to first administration of study drug the baseline result will be missing.

Post-baseline

For safety and efficacy evaluations all assessments after the first administration of study drug are defined as “post-baseline” assessment.

Change and percent change from baseline for continuous parameter.

Change from baseline and percent change from baseline will only be summarized for subjects with both baseline and post-baseline values and will be calculated as:

change from baseline = post-baseline value – baseline value

percent change from baseline = $100 * \text{change from baseline} / \text{baseline value}$.

For summary statistics the raw values (and not imputed values) will be used.

Study periods and date of last contact

The overall observation period will be divided into three mutually exclusive segments:

- A screening phase of up to 4 weeks
- A double-blind treatment phase starting with first dose of study drug at Visit 101 and covering 12 weeks of treatment.
- A double-blind treatment withdrawal phase for one week starting after 12 weeks of treatment with Visit 201.

Inferential analysis will be performed on either only treatment phase or on both treatment and treatment withdrawal phase separately. It is never the case that both phases will be pooled together.

Visit windows

Visit windows will be applied for all measurements except NRS scores. The definition of seamless windows can be found in the following [REDACTED] location [REDACTED]

[figure not shown]
[REDACTED] The most recent version of this document available before the database lock will be used to determine the visit windows for baseline and post baseline visits and treatment discontinuation visit mapping.

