2.8.3 Laboratory data

The summary of laboratory evaluations will be presented for three groups of laboratory tests: Hematology, Chemistry and Urinalysis.

The number and percentage of patients with newly occurring or worsening laboratory abnormalities meeting the clinically notable criteria at any post-baseline visit will be summarized by laboratory parameter. For a patient to meet the criterion of a newly occurring clinically notable value, the patient needs to have a baseline value that is not clinically notable for that parameter. For a patient to meet the criterion of a worsening clinically notable value, the patient needs to have a baseline value that is clinically notable and also have a worse post-baseline value. For patients with missing baseline value, any post-baseline notable value will be considered as newly occurring.

Incidence of newly occurring liver enzymes abnormalities and renal events will be summarized using the number and percentage of patients by treatment group. Notable laboratory values will be listed.

Laboratory assessments performed at the follow-up visits in the scope of the USM will not be included in the summaries but will be listed. That means, assessments reported 21 days after end of study date will not be included in the summary tables.

Liver function tests (LFT)

To evaluate potential drug-induced liver injury, the number and percentage of patients with newly occurring or worsening abnormalities in liver function tests at any time post-baseline will be summarized by treatment. The same approach as for notable laboratory values will be used to define newly occurring or worsening abnormalities in liver function tests.

When a criterion contains multiple laboratory parameters, the criterion will only be considered to have been met when all conditions occur at the same time (i.e., within the same sample). A case where all criteria are met at a post-baseline time point will be considered as newly occurring if the criteria are not met at baseline and will be considered as worsening if the criteria are met at baseline and at least one component is worsening from baseline irrespective of whether the other(s) are better.

Listings of patients with clinically notable LFT values will be provided.

The same analysis will be repeated for the Treatment withdrawal epoch.

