2.8.4 Other safety data

2.8.4.1 ECG

The (uncorrected) QT interval will be corrected according to Fridericia's formulae. The incidence rates of newly occurring or worsening clinically notable ECG abnormalities will be summarized. The same approach as for notable laboratory values will be used to define a newly occurring notable QTc value and a worsening notable QTc value. Notable ECG values will be listed.

Notable criteria are:

- QTcF > 500 msec or
- increase from baseline > 60 msec

If the single ECG shows a QTcF > 500 ms (males or females), 2 additional ECG replicates should be recorded to confirm the safety findings and copies forwarded to the central ECG laboratory for assessment. The results from those triplicate ECGs will be averaged and analysed as one value for summary and notable tables.

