5.3 Laboratory parameters derivations

Liver events defined by laboratory parameter abnormalities (additional non-lab criteria as provided in the protocol are ignored):

- ALT or AST $> 5 \times$ ULN
- ALP $> 2 \times$ ULN
- TBL $> 2 \times$ ULN
- ALT or AST $> 3 \times$ ULN and INR > 1.5
- ALT or AST $> 3 \times$ ULN and TBL $> 2 \times$ ULN AND ALP $\leq 2 \times$ ULN (Potential Hy's Law cases)
- ALT or AST $> 3 \times$ ULN

Renal events defined by laboratory parameter abnormalities (additional non-lab criteria as provided in the protocol are ignored):

- Serum creatinine increase 25 – 49% compared to baseline
- Serum creatinine increase $\geq 50\%$ compared to baseline
- New dipstick proteinuria $\geq 1+$
- New dipstick glycosuria $\geq 1+$ not due to diabetes
- New dipstick hematuria $\geq 1+$ not due to trauma
- Albumin- or Protein-creatinine ratio increase ≥ 2 -fold
- Albumin-creatinine ratio (ACR) ≥ 30 mg/g or ≥ 3 mg/mmol
- Protein-creatinine ratio (PCR) ≥ 150 mg/g or > 15 mg/mmol

Laboratory results will be reported in SI units.

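### The SAP 2.1.1 safety baseline shuts out Screening-visit values and disagrees with its own missing-baseline sentence, so a few patients could be misclassified on urine, QTcF and change-based criteria

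*SAP*

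**What the plan says.** SAP 2.1.1 covers safety and efficacy with one definition: "the last available assessment (either scheduled or unscheduled) before the first administration of study drug and after the screening visit is defined as" the baseline assessment. It continues: "If patients have no value prior to first administration of study drug the baseline result will be missing". It also states: "Change from baseline and percent change from baseline will only be summarized for subjects with both baseline and post-baseline values".

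For notable laboratory values, SAP 2.8.3 says that to count as newly occurring "the patient needs to have a baseline value that is not clinically notable for that parameter". It then makes an exception: "For patients with missing baseline value, any post-baseline notable value will be considered as newly occurring". The approach is carried over to liver tests ("The same approach as for notable laboratory values will be used to define newly occurring or worsening abnormalities in liver function tests") and, in SAP 2.8.4.1, to QTc ("The same approach as for notable laboratory values will be used to define a newly occurring notable QTc value"). No missing-baseline rule is stated for vital signs or weight.

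Several safety criteria need a baseline value. SAP 5.3 lists "Serum creatinine increase 25 – 49% compared to baseline", a rise of 50% or more, and a two-fold rise in albumin- or protein-creatinine ratio (ACR/PCR). SAP 2.8.4.1 has a QTcF rise above 60 msec. SAP 2.8.4.2 requires a change from baseline for pulse, blood pressure and weight.

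Protocol Table 6-1 schedules hematology and chemistry, urinalysis, ECG, vital signs and weight both at Visit 1 and on Day 1 (Visit 101). Neither document gives a fallback to the Visit 1 value.

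**The concern.** A patient who reaches dosing should already have a Visit 1 value for the scheduled safety tests. If the Day 1 value is absent and nothing was measured in between, the definition sets that value aside. Two errors then run in opposite directions in the same patient: a finding already on record at Visit 1 can be reported as new, and a genuine rise from Visit 1 cannot be reported at all.

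The affected tables carry more weight than usual. The study stopped early under urgent safety measures, and SAP section 4 drops the summary statistics for laboratory data, vital signs and ECG intervals, along with the laboratory shift tables. Incidence tables of notable values are most of what is left for these data.

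**Working it through.** The plan gives no figure to reproduce. The check applies its rules to example patients and then bounds the size.

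**1. The two baseline sentences.** Take a patient with a Visit 1 value and nothing else before the first dose. The defining sentence requires a time after the Screening visit, so there is no baseline. The next sentence makes baseline missing only if no value precedes the first dose, and this patient has one. Two programmers could build different tables from this paragraph. Steps 2 to 4 follow the defining sentence.

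**2. Threshold criteria.** Example (assumed values): QTcF 510 msec at every available pre-dose assessment and 510 msec later, limit 500 msec.

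| Pre-dose data | Baseline as written | Class as written | Class with Visit 1 fallback |
|---|---|---|---|
| Day 1 present | 510 | neither new nor worsening | same |
| Day 1 missing, unscheduled test after Visit 1 | 510 | neither new nor worsening | same |
| Day 1 missing, Visit 1 only | missing | newly occurring | neither new nor worsening |

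Only the third row goes wrong.

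**3. Change-based criteria, third-row patient (assumed values).**
- Creatinine 80 at Visit 1, later 130: not evaluable as written. With the fallback, (130 − 80)/80 = 62.5%, which meets the 50% criterion.
- QTcF 410 msec at Visit 1, later 480: not evaluable as written. With the fallback, 480 − 410 = 70 msec, which meets the 60 msec criterion.

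**4. Denominator.** SAP 2.1 bases percentages on the number of patients in the relevant population or subgroup, and SAP 2.8 names the safety population. No subgroup with an available baseline is defined. A missing category may be shown, but that does not alter the denominator. A patient who cannot be evaluated therefore counts as event-free.

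**5. Which parameters.**
- Liver: exclusion 13 bars ALT or AST at or above 1.5 × ULN, and bilirubin or ALP above ULN, at Screening. The SAP 5.3 limits start at 3 × ULN for ALT/AST and 2 × ULN for ALP and bilirubin. A falsely new liver case from a Visit 1 abnormality would need an eligibility violation.
- Hematology: exclusion 14 sets Screening limits, and the notable limits are in the laboratory manual, which is not available. No overlap can be shown.
- Urine and ACR/PCR: no Screening exclusion on these findings appears, all patients are diabetic, and eGFR down to 40 is admitted. A prior abnormality is plausible. The visible schedule shows a dipstick at Visit 1 but no ACR/PCR, so the fallback helps there only if a ratio was measured.
- QTcF: exclusion 3 gives no numeric limit.

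**6. Size.** Patients randomised: 137 (SAP, Amendment 1). The share m with no baseline and the share p of those with a persisting abnormality are not given, so both are assumptions.
- Without a baseline, 137 × m: 1.4 at 1%, 6.9 at 5%, 13.7 at 10%.
- Falsely new per parameter, 137 × m × p: 137 × 0.01 × 0.05 = 0.07 at the low end; 137 × 0.05 × 0.20 = 1.4 in the middle; 137 × 0.10 × 0.50 = 6.9 at the high end.
- Per arm at 1:1: 137/2 ≈ 68. One patient is 1/68 ≈ 1.5 percentage points.

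**The case against.** The strongest reply is that the trigger is rare and little is lost.
- Day 1 ECG, vital signs and blood samples are sequenced before study drug (Table 6-1, footnote 6), and clinically significant ECG findings at randomisation must be discussed with the sponsor before dosing (protocol 6.5.5).
- Unscheduled tests after Visit 1 count as baseline, and protocol 5.5.1 encourages laboratory repeats within the screening phase.
- The summaries are descriptive, and the rule is the same in both blinded arms.
- Clinically significant findings are reported as adverse events whatever the baseline, and notable values are listed.
- Insisting on a recent baseline is defensible for a criterion as fine as a 25% creatinine rise.
- The external visit-window document was not available and may map visits differently.

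All of this bears on size, and most of it stands. It does not remove the conflict between the two sentences. Nor do listings recover a change-based event, because without a baseline the value is never flagged as notable on that criterion.

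A reader might infer more than the documents support:
- That any missed Day 1 test causes the error. It does not if a later pre-dose test exists.
- That liver and hematology counts are inflated. Exclusion 13 all but rules this out for liver, and nothing shows it for hematology.
- That the plan treats every missing baseline as normal. The rule is stated for notable laboratory values, liver tests and QTc only.
- That the distortion is as large as the event rates themselves. Neither document gives event rates or a missing-data rate.

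**Conclusion.** The point holds in a narrow form. SAP 2.1.1 contradicts itself for a patient whose only pre-dose value is from Visit 1. Under its defining sentence, such a patient can be counted as a new case for a prior urine, ACR/PCR or QTcF abnormality. The same patient cannot meet the creatinine, ACR/PCR two-fold, QTcF +60 msec, vital-sign or weight criteria, but remains in the denominator.

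Expected impact is low. The number of such patients is unknown and probably small, and misclassified patients are fewer still, since each also needs a persisting abnormality or a real change. The 1.5-point figure assumes that all 137 randomised patients were dosed and split evenly; the size of the safety population is not given. This is a cheap improvement and not a threat to the safety conclusions.

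**What to change.** Amend SAP 2.1.1 and 2.8.3 as follows.
1. For safety parameters, define baseline as the last non-missing value before the first dose, using the Screening-visit value when no later pre-dose value exists. Keep the restriction to assessments after the Screening visit for the efficacy scales.
2. Apply the missing-baseline rule of 2.8.3 only when no pre-dose value exists at all.
3. Exclude patients with no pre-dose value from the denominator of change-based criteria, and show their number.
4. Flag in the listings any patient whose baseline is a Screening fallback.

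The cost is a few sentences and a small programming change, with no new data. The drawback is age: Table 6-1 allows Visit 1 as early as Day −35, so a fallback baseline may be up to five weeks old. That is why the flag is needed.
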